17. APPENDIX F – REDO PROCEDURAL CRF

1

2 **1. SYNOPSIS**

3 This prospective, single-center observational study aims to compare the clinical performance,
4 workflow efficiency, and electrophysiological metrics of two commercially available, high-
5 density multielectrode mapping catheters (Ostaray and Optrell) in patients undergoing catheter
6 ablation for complex atrial arrhythmias.

7 The primary focus is to determine if the real-time vector propagation capabilities of the Optrell
8 catheter combined with V8 software can accurately confirm conduction block across linear
9 ablation lesions without the need for full-chamber activation remapping, which is the current
10 standard of care. A secondary focus will pair-compare the bipolar voltage amplitude distributions
11 recorded by both catheters, given their differing electrode sizes and spacing

12

13 **2. BACKGROUND AND RATIONALE**

14 **2.1 The Clinical Challenge of Conduction Block Assessment**

15 Catheter ablation is a cornerstone therapy for atrial fibrillation (AF) and atrial flutter. In patients
16 with persistent AF or specific anatomical flutters, the creation of linear ablation lesions (e.g., roof
17 line, posterior wall isolation, cavotricuspid isthmus [CTI] line, or mitral isthmus line) beyond
18 standard Pulmonary Vein Isolation (PVI) is often clinically indicated.

19 A critical determinant of procedural success and long-term freedom from arrhythmia is the
20 achievement of bidirectional conduction block across these lines. Currently, confirming this block
21 requires time-consuming, full-chamber activation remapping using a standard high-density
22 catheter (such as the Ostaray).

23 **2.2 The Investigational Approach**

24 The Optrell catheter, when integrated with V8 mapping software, offers real-time visualization of
25 electrical propagation vectors. We hypothesize that this directional vector mapping allows
26 operators to immediately and accurately identify the presence or absence of conduction block
27 across a linear lesion. Validating this hypothesis could eliminate the need for complete chamber
28 remapping, significantly streamlining procedural workflow and reducing procedure times.

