4. STUDY ENDPOINTS

4.1 Primary Endpoints

- **Concordance:** Percentage of agreement (presence vs. absence of bidirectional block) between the Optrell real-time vector assessment and standard activation remapping on a per-line basis.
- **Workflow Efficiency:** Difference in time (in minutes) required to confirm conduction block status using the Optrell vector method versus full activation mapping.

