6.2 Intra-Procedural Workflow

The procedure will be performed under general anesthesia. Following standard venous access, transseptal puncture will be performed to access the left atrium. Systemic anticoagulation with intravenous Heparin will be administered and maintained to achieve an activated clotting time (ACT) >300 seconds.

• Phase 1: Voltage Mapping (coronary sinus pacing)

Following transseptal access and prior to ablation, a left atrial 3D map using TPI with left atrial voltage mapping will be performed using the Octaray catheter. The Octaray catheter will then be exchanged for the Optrell catheter, and a second high-density voltage map will be acquired on the

same 3D map (remap). A high density Multipolar map using parallel mapping will be performed in the same time with the Optrell catheter. All the maps need to have a fill threshold $\leq 3\text{mm}$ to allow sufficient density.

For patient in atrial fibrillation, an electrical cardioversion will be performed and mapping will be performed during coronary sinus pacing. For patient in sinus rhythm, mapping will be performed during coronary sinus pacing. For patient in atrial flutter, mapping will be performed in arrhythmia.

• **Phase 2: Ablation:**

The operator will perform PVI and any clinically indicated linear lesion sets according to standard of care using either radiofrequency or pulsed field ablation energy.

• **Phase 3: Conduction Block Assessment**

After completing the ablation phase, conduction block across lines will be assessed using both methods:

- *Optrell Vector Assessment*: Real-time evaluation of conduction vectors using the Optrell catheter and V8 software. The time to determination, from the beginning of the mapping (pacing start) to block confirmation, and the binary result (block vs. no block) will be recorded.
- *Standard Activation Mapping*: Creation of a full activation map using the Octaray catheter (often requiring pacing maneuvers) to establish the gold-standard confirmation of block. Time to determination, from the beginning of the mapping to block confirmation, and the binary result will be recorded.

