8. STATISTICAL CONSIDERATIONS

8.1 Sample Size

A sample size of 30 patients is targeted. Because each patient will likely contribute multiple mapped regions and ablation lines (e.g., roof line, posterior wall, CTI), this will yield a robust number of paired observations for both voltage and block concordance analyses.

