Optrell bipolar	 Yes  No	 Yes  No	_____ points
Optrell multipolar	 Yes  No	 Yes  No	_____ points

SECTION 3: PHASE 2 - ABLATION DETAILS

Variable	Data Entry
Ablation Energy Used	 RFA  PFA
PVI Performed?	 Yes  No
PVI Successfully Achieved?	 Yes  No
First Pass Isolation ?	 Yes  No
Linear Lesions Created (Check all that apply)	 Roof Line  Posterior Wall Isolation (PWI)  Cavotricuspid Isthmus (CTI)  Mitral Isthmus Line  Other: _____

SECTION 4: PHASE 3 - CONDUCTION BLOCK ASSESSMENT

(Complete this sub-section for EVERY linear lesion created. See Section 4b, 4c and 4d. Duplicate if necessary.)

Line Checked	 Roof Line  Posterior Wall Isolation (PWI)  Cavotricuspid Isthmus (CTI)  Mitral Isthmus Line  Other:	
Ablation Energy Used	 RFA  PFA	

Assessment Method	Time to Verify Block	Block Confirmed?
Optrell Vector Assessment (time to assess block by moving the catheter across the line to review vectors)	___ min : ___ sec	 Yes  No
Octaray Activation Mapping (time to create an activation map sufficient to determine presence or absence of block)	___ min : ___ sec	 Yes  No

Concordance for this line: ☐Yes (Methods agree) ☐No (Methods disagree)

Explain:_____

SECTION 5: ACUTE PROCEDURAL COMPLICATIONS (completed at hospital discharge)

Variable	Data Entry
None	
Pericardial Effusion / Tamponnade	
Stroke / TIA	

CONFIDENTIAL

Variable	Data Entry
Vascular Complication requiring intervention	
Phrenic Nerve Injury	
Prolongation of Hospitalization (>24 hours beyond the expected post-procedural course)	
Esophageal injury	

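### Primary time endpoint: the forms have no rule for an Octaray map shared by several lines, and entering its time once per line would overstate the saving

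*Protocol*

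**What the plan says.** Section 4.1 defines the workflow endpoint as "Difference in time (in minutes) required to confirm conduction block status using the Optrell vector method versus full activation mapping". It attaches a per-line basis to the concordance endpoint only. The time endpoint names no unit, and neither does the paired t-test or Wilcoxon test in 8.2.

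The comparator covers a whole chamber. The Synopsis asks whether block can be confirmed "without the need for full-chamber activation remapping", and 3.1 uses the same full-chamber comparator. Phase 3 of 6.2 assesses block across lines, in the plural, by "Creation of a full activation map using the Octaray catheter (often requiring pacing maneuvers) to establish the gold-standard confirmation of block", a single map. Its time is defined as "Time to determination, from the beginning of the mapping to block confirmation". Section 7.4 repeats this for redo procedures and has each earlier line's durability taken from the standard map, again in the singular. Section 6.3 describes one added mapping sequence after ablation. Section 8.1 expects most patients to contribute more than one line.

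The recording unit is the line. Appendix D, Section 4 instructs "Complete this sub-section for EVERY linear lesion created", with printed repeats 4b to 4d. Appendix F does the same in Sections 3 to 3d and 5 to 5d. Each block has one Octaray time and one Optrell time. The Optrell label refers to moving the catheter across that line. The Octaray label refers to a map good enough to decide on block, which is not the same as a full map. No field holds a map-level time, a map identifier, or the lines that a map served.

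**The concern.** The benefit the study hopes to show is procedure time saved by omitting a full-chamber remap. For one chamber, that is the time of the map minus the total vector time over all the lines the map would have settled. A form that pairs map time with vector time line by line measures this only when each line has its own map.

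When two or more lines are read from one map, the operator must choose a convention: repeat the whole map time, enter only the extra minutes, or read a running clock. The protocol gives no rule, and the forms do not show which choice was made. The result of a primary endpoint could therefore depend on a data-entry habit. An analyst working from these forms could not reliably undo it.

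**Working it through.** The plan has no figure of its own to reproduce. Section 8.1 gives 30 patients without a time difference, standard deviation or power, and no section gives the duration of a map or of a vector assessment. All times below are assumptions.

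**Notation.** T = minutes for one Octaray map shared by the lines in a chamber; v = vector minutes per line; k = lines read from that map (Appendix D prints four line forms). A positive saving favours the vector method.

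**If T is entered on every line's form**
- Recorded saving per line: T − v
- Real saving per chamber: T − kv
- Real saving per line: T/k − v
- Overstatement per line: (T − v) − (T/k − v) = T(k − 1)/k
- The sign is wrong when T − v > 0 and T − kv < 0, that is, T/k < v < T

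| T | v | k | Recorded per line | Real per chamber | Real per line | Overstatement per line |
|---|---|---|---|---|---|---|
| 10 | 2 | 1 | +8 | +8 | +8 | 0 |
| 10 | 2 | 2 | +8 | +6 | +3 | 5 |
| 10 | 2 | 3 | +8 | +4 | +1.33 | 6.67 |
| 10 | 4 | 3 | +6 | −2 | −0.67 | 6.67 |
| 15 | 4 | 3 | +11 | +3 | +1 | 10 |
| 5 | 2 | 3 | +3 | −1 | −0.33 | 3.33 |

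**Effect on the test.** In 2,000 simulated studies of 30 patients with T averaging 10 (SD 2.5), v averaging 4 (SD 1) and k = 3, the mean recorded saving was +6.0 minutes per line. A paired t-test on lines favoured the vector method significantly in every run. The mean real saving was −2.0 minutes per patient.

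**Other ways of filling in the form**
- *Separate map for each line:* recorded and real savings are both T − v, so there is no bias.
- *Only the extra minutes for later lines:* with T = 10, v = 3, k = 3 the entries are 10 − 3 = +7, then 0 − 3 = −3 twice. The mean, (7 − 3 − 3)/3 = +0.33, equals T/k − v. Repeating T gives +7, +7, +7 for the same procedure, which a signed-rank test treats very differently.
- *One growing map, with line j read at jT/k:* the mean recorded saving is T(k + 1)/(2k) − v. For T = 10, v = 4, k = 3 it is 6.67 − 4 = +2.67, against a real −0.67 per line.
- *T repeated, and vector time also cumulative from one pacing start:* the mean recorded saving is T − v(k + 1)/2 = 10 − 8 = +2. The last line gives the real chamber value, 10 − 12 = −2.

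**The case against.** A reader might infer that one map always serves every line, that its full time is copied to each form, and that the saving is therefore overstated. The protocol does not say this. Section 6.2 notes that the Octaray map often needs pacing maneuvers, which may mean separate maps for separate lines. The Octaray label on the form can be read as a clock specific to the line. Section 6.2 starts the Optrell clock at the start of pacing, so vector times may also be cumulative. A CTI line and a left atrial line need not share a map; Appendix D has separate LA and RA map rows. These points stand, and they make the bias conditional.

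The sign reversal is not the typical case either. With T of 6, 10 or 15, v of 1.5, 3 or 5 and k of 1, 2 or 3, the real chamber saving is negative in 4 of 27 combinations and zero in 3. Section 9.2 expects about 15 minutes of prolongation in total. If that covers a pre-ablation Optrell map of about T plus the vector assessments, T + kv = 15, and reversal (kv > T) requires T below 7.5. T = 6, v = 3, k = 3 fits, recording +3 per line against a real −3 per chamber. T = 10, v = 4, k = 3 would need 22 minutes. This makes reversal less likely but does not remove the overstatement, which does not depend on v.

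An overstatement of (k − 1)T would apply only to a sum over lines, which 8.2 does not plan. Finally, the pairing unit could be settled in an SAP that is not shown. That is fair for the analysis, but an SAP cannot supply a map identifier that the forms never collected.

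**Conclusion.** The point holds as a conditional defect in how a primary endpoint is recorded. The protocol's wording makes a shared map likely in patients with several lines in one chamber, and the forms provide only line-level Octaray times with no rule for sharing. If a shared map's time is repeated, the saving is overstated by T(k − 1)/k minutes per line: half the map time for two lines, two thirds for three. The sign is wrong only when v lies between T/k and T. There is no bias with one line per chamber or a separate map for each line, and less if the vector clock is also cumulative. The formulas follow from the form layout; the minutes are illustrative because the protocol gives none. The documents do not establish that the saving will in fact be overstated. They do leave the endpoint open to it without a reliable way to detect or correct it from the forms.

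**What to change.** - **Appendices D and F:** add a map-level row recording the start and stop of each Octaray map once, by chamber and pacing site, with the lines read from it. Keep both block results and the vector time for each line. Keep a per-line Octaray time only where that line had its own map.
- **Sections 6.2 and 7.4 and the form labels:** use one definition for each clock. State whether the Octaray clock stops at a full map or at a map sufficient for a decision, and whether the Optrell clock starts at pacing or at movement across the line.
- **Sections 4.1 and 8.2:** define the time difference per chamber within patient, as total Octaray map time minus the sum of the Optrell vector times for the same lines.

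This costs one form row and a few sentences, with no extra mapping. It leaves fewer time pairs and probably a smaller apparent saving. It should be in place before data collection starts, because the missing map-level information cannot be reliably rebuilt from line forms.

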3.2 Secondary Objectives

- To perform a paired comparison of bipolar voltage amplitude distributions in the left atrium recorded by the Optrell versus the Octaray catheter during CS pacing before and after ablation.
- To perform a paired comparison of multipolar voltage amplitude distributions in the left atrium recorded by the Optrell versus bipolar voltage with the Octaray catheter during CS pacing before and after ablation.
- To evaluate the safety profile of the dual-catheter mapping approach.
- To assess long-term clinical outcomes, specifically the 12-month freedom from recurrent atrial tachyarrhythmias (AF, atrial flutter, or atrial tachycardia).

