4.2 Secondary Endpoints

- **Bipolar Voltage Correlation:** Statistical correlation and evaluation of systematic bias (limits of agreement) between the bipolar voltage amplitudes recorded by the two catheters in matched anatomical regions.
- **Multipolar Voltage Correlation:** Statistical correlation and evaluation of systematic bias (limits of agreement) between the multipolar voltage amplitudes recorded by the Optrell catheter and the bipolar voltage amplitudes recorded by the Octaray catheter in matched anatomical regions
- **Clinical Efficacy:** Freedom from any documented atrial tachyarrhythmia lasting ≥ 30 seconds at 1, 3, 6, 9, and 12 months.
- **Safety:** Incidence of acute procedural complications prior to hospital discharge.

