- 185 • Any other serious adverse event related to the procedure

186

187 **Safety Follow-Up Period**

188 Formal protocol-mandated safety follow-up will extend through 7 days after the procedure or until
189 hospital discharge, whichever occurs later.

190 All AEs and SAEs occurring during this period will be documented in the CRF and reviewed by
191 the Medical Monitor.

192

193 **7.2 Clinical Follow-Up and Rhythm Monitoring**

194 Patients will undergo highly structured longitudinal follow-up to monitor for clinical and
195 subclinical arrhythmia recurrence and symptom status.

196 **Clinic Visits:**

CONFIDENTIAL

Patients will be evaluated at the following time points after the ablation procedure:

- 1 month \pm 14 days
- 3 months \pm 30 days
- 6 months \pm 30 days
- 9 months \pm 30 days
- 12 months \pm 30 days

Visits at 3 and 12 months will be conducted in person, while other visits may be conducted in person or via telemedicine, depending on clinical circumstances.

During these visits, the following information will be collected:

- Symptoms suggestive of arrhythmia recurrence
- Medication use, including antiarrhythmic drugs and anticoagulation
- Interval hospitalizations or cardiovascular events
- Standard ECG documentation when available

Rhythm Monitoring:

To systematically detect symptomatic and asymptomatic arrhythmia recurrence, patients will undergo scheduled ambulatory rhythm monitoring during follow-up.

A minimum of three 48-hour Holter monitors will be performed at:

- 3 months \pm 30 days
- 6 months \pm 30 days
- 12 months \pm 30 days

Additional rhythm monitoring (Holter, event monitor, or ECG) may be performed at the treating physician's discretion if symptoms suggest arrhythmia recurrence.

Recurrence of atrial arrhythmia will be defined as documented AF or atrial tachycardia lasting \geq 30 seconds after the standard 2-month blanking period.

Community-Based Testing: To facilitate protocol compliance, both the 12-lead ECGs and the 24-hour Holter monitors may be performed locally at the patient's primary care clinic (Kupat Holim). The study coordinator is responsible for retrieving and analyzing these community-based reports and logging the data into the study database.

228

229 **7.3 Post-Procedure Antiarrhythmic Drug Management**

230 The use of AADs following the ablation procedure will be at the discretion of the treating
231 electrophysiologist and managing physician, in accordance with routine clinical practice.

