232 Continuation, initiation, or discontinuation of AAD therapy during follow-up will not be dictated
233 by the study protocol. All AAD use will be prospectively documented, including drug type, dosing,
234 changes, discontinuation, and replacement. This information will be incorporated into the clinical
235 database and considered in exploratory analyses of arrhythmia recurrence.

236

237 **7.4 Redo Procedures and Lesion Durability Assessment**

238 Any documented recurrence of atrial flutter or AF will prompt consideration for a redo procedure,
239 as clinically indicated.

240 If a redo procedure is performed during the 12-month follow-up period, the index protocol
241 performed again: a left atrial 3D map using TPI with left atrial voltage mapping will be performed
242 using the Octaray catheter. The Octaray catheter will then be exchanged for the Optrell catheter,
243 and a second high-density voltage map will be acquired on the same 3D map (remap). A high
244 density Multipolar map using parallel mapping will be performed in the same time with the Optrell
245 catheter. All the maps need to have a fill threshold ≤ 3 mm to allow sufficient density. For patient
246 in atrial fibrillation, an electrical cardioversion will be performed and mapping will be performed
247 during coronary sinus pacing. For patient in sinus rhythm, mapping will be performed during
248 coronary sinus pacing. For patient in atrial flutter, mapping will be performed in arrhythmia.

249 • **Block Assessment:** Prior to delivering any new ablation, the operator must re-assess
250 conduction block across all linear ablation lesions created during the index procedure.

251 **Gold Standard Block Assessment:** Creation of a full activation map using the Octaray catheter
252 (often requiring pacing maneuvers) to establish the gold-standard confirmation of block. Time to
253 determination, from the beginning of the mapping to block confirmation, and the binary result will
254 be recorded.

255 **Optrell Vector Assessment:** Real-time evaluation of conduction vectors using the Optrell catheter
256 and V8 software. The time to determination, from the beginning of the mapping (pacing start) to
257 block confirmation, and the binary result (block vs. no block) will be recorded.

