Optrell Vector Assessment (time to assess block by moving the catheter across the line to review vectors)	____ min : ____ sec	 Yes  No
Octaray Activation Mapping (time to create an activation map sufficient to determine presence or absence of block)	____ min : ____ sec	 Yes  No

Concordance for this line: ☐Yes (Methods agree) ☐No (Methods disagree)

Explain:_____

16. Appendix E – Follow-Up CRF**SECTION 1: VISIT INFORMATION**

Variable	Data Entry
Date of Procedure	_____
Patient MRN	_____
Follow-Up Visit	 1 Mo  3 Mo  6 Mo  9 Mo  12 Mo
Visit Type	 In-Person  Virtual (Telehealth)
Visit Date	_____
Within protocol window?	 Yes  No (Protocol Deviation)

SECTION 2: RHYTHM STATUS & RECURRENCE

(Arrhythmia \geq 30 sec beyond blanking period of 2 months from last procedure)

Variable	Data Entry
Documented Atrial Arrhythmia Since Last Visit?	 Yes  No
Type of Arrhythmia Documented	 AF  AT  Typical Flutter  Atypical Flutter
Symptomatic During Episode?	 Yes  No
Date of First Recurrence	_____
Number of Episodes	 1  1-3  3-5  >5

SECTION 3: RHYTHM MONITORING

Variable	Data Entry
12-Lead ECG Performed?	 Yes (Date: _____)  No
ECG Result	 No Arrhythmia  AF  AT  Flutter
48-Hour Holter Performed?	 Yes (Date: _____)  No
Testing Location	 Hospital Clinic  Kupat Holim (Community)
Holter Result	 No Arrhythmia  AF  AT  Flutter

SECTION 4: CLINICAL EVENTS SINCE LAST VISIT

Variable	Data Entry
Hospitalization	 Yes  No

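### The 12-month freedom-from-arrhythmia endpoint is defined inconsistently on flutter, blanking and time points, and two of the rules, read literally, can raise the reported figure

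*Protocol*

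**What the plan says.** Freedom from arrhythmia is a secondary endpoint. Five places in the protocol bear on it.

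- **Section 3.2** states the objective as "12-month freedom from recurrent atrial tachyarrhythmias (AF, atrial flutter, or atrial tachycardia", so flutter and AT are named separately.
- **Section 4.2** defines the endpoint: "Freedom from any documented atrial tachyarrhythmia lasting" at least 30 seconds, "at 1, 3, 6, 9, and 12 months". It names no blanking period.
- **Section 7.2** gives the formal definition: "Recurrence of atrial arrhythmia will be defined as documented AF or atrial tachycardia lasting" at least 30 seconds, "after the standard 2-month blanking period". Flutter is not named, and the procedure from which blanking runs is not stated.
- **Appendix E, Section 2** restricts the follow-up form to episodes of at least 30 seconds "beyond blanking period of 2 months from last procedure". It has separate boxes for AF, AT, typical flutter and atypical flutter. Each form asks about the interval since the previous visit and has a field for the date of first recurrence.
- **Section 7.4** has a recurrence of flutter or AF lead to a redo being considered, and provides for redo within the endpoint window: "If a redo procedure is performed during the 12-month follow-up period".

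Section 8.2 plans a Kaplan-Meier estimate of freedom at 12 months.

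**The concern.** A Kaplan-Meier estimate needs one event definition, one time origin and a date for each event. Here the event depends on which section is followed, and the form on which it is recorded uses a time origin that can move.

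The patients affected are not a random subset. Patients with flutter are eligible, and the study is about linear lesions, so flutter is not a marginal category. A patient whose recurrence leads to a redo has had a recurrence judged to need another ablation. If either group drops out of the event count, the reported freedom no longer describes rhythm after the study ablation. The 1-month figure would also carry no information if the blanking of 7.2 is applied to it.

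**Working it through.** The protocol gives no expected recurrence rate, redo rate or event count, and 30 patients (section 8.1) is a bare target. There is no figure to reproduce. The check sets the texts side by side, then uses date arithmetic and an illustration of size.

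**Step 1: the definitions compared.**

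| Place | Arrhythmias counted | Blanking | Blanking runs from |
|---|---|---|---|
| 3.2 | AF, flutter, AT | none named | – |
| 4.2 | any atrial tachyarrhythmia | none named | – |
| 7.2 | AF, AT | 2 months | not stated |
| Appendix E | AF, AT, two flutter types | 2 months | last procedure |

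Flutter cannot simply be read into AT in 7.2, because 3.2 and Appendix E list the two separately. On the starting point of blanking, Appendix E fills a gap in 7.2 rather than contradicting it, but it is the only place that supplies one.

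**Step 2: the 1-month time point.** The visit window in 7.2 is 1 month ± 14 days. With 30-day months that is day 30 − 14 = 16 to day 30 + 14 = 44. Blanking ends at about day 60. Since 44 < 60, the whole window is blanked, and freedom at 1 month is 100% by definition under 7.2. Under 4.2 read alone it is not.

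**Step 3: the restart of blanking.** Take a recurrence on day 150, a redo on day 170 and the 6-month visit at about day 180. At that visit the last procedure is the redo, so blanking runs to about day 170 + 60 = 230. The day-150 episode fails the form's rule. If the same recurrence had been entered at an earlier visit, its date would stand. The event is lost only when recurrence and redo fall between the same two visits, or when the rule is applied backwards to earlier entries.

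**Step 4: whether the date survives elsewhere.** In Appendix E, hospitalization and cardioversion are undated yes/no items, and the redo item dates the redo. Appendix F records the arrhythmia type but has no field for the date of the recurrence that led to the redo. ECG and Holter entries are dated, but Holters are scheduled only at 3, 6 and 12 months. Some events could be recovered; no field is designed to do so.

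**Step 5: size.** One patient is 1/30 = 3.3 points (no censoring). All rates below are assumptions.

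- *Blanking restart.* Let R be true 12-month recurrence, q the share of recurrers who have a redo, and e the share of those whose recurrence and redo fall between the same two visits. Reported freedom = 1 − R + R·q·e.
  - Low: R = 0.20, q = 0.25, e = 0.3 gives a rise of 0.015, or 1.5 points.
  - Middle: R = 0.30, with q 0.25–0.5 and e 0.3–0.6, moves 70% to between 72% and 79%.
  - High: R = 0.50, q = 0.5, e = 0.6 gives 0.15, or 15 points.
  - With e = 0 the rise is 0.
- *Plausibility of e.* With recurrence uniform over months 2–12 and an exponential delay to redo with mean 0.5, 1, 2 or 3 months, the redo precedes the next visit in 81%, 65%, 46% or 35% of cases. The 15 points are therefore the top of this grid, not a bound.
- *Flutter not counted.* With s the share of recurrers who have flutter only, reported freedom = 1 − R(1 − s). At R = 0.30, s = 0.1 gives 73% and s = 0.5 gives 85%, against 70%.

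**The case against.** The strongest reply has five parts.

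- The Appendix E wording is a parenthetical instruction on a form. Sections 4.2, 7.2 and 8.2 never restart blanking at a redo. Because patients with earlier ablations may enrol, the last procedure might mean the study ablation as opposed to those earlier ones. That reading is possible, but the form does not state it, and a coordinator completing it after a redo would naturally take the redo as the last procedure.
- Flutter is missing from one sentence only. The endpoint text in 4.2 covers it and the form collects it, so bias arises only if the analyst follows 7.2 over 4.2. This stands, and it is why the effect is conditional.
- Events remain partly traceable through dated ECGs and Holters and the redo forms. This also stands, within the limits shown in the working.
- Whether a redo is an event, a censoring point or a restart is commonly left to the SAP, which is not at hand. That silence is not held against the protocol. An SAP cannot, however, restore a date that the form told staff not to enter.
- No passage commits the study to an estimate for the index procedure alone. Counting from the index study procedure is therefore a recommended choice, not one the text dictates.

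A reader might go further and infer that 12-month freedom is overstated, and that all three conflicts push it up. The documents do not support either. The first two conflicts can raise the figure only if the literal rule is followed and the event is not recovered. The 1-month conflict does not touch the 12-month estimate.

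**Conclusion.** Wrong as written, of moderate severity. The conflicts on flutter, on blanking and on the 1-month time point are plain from the text and need no assumption.

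Their effect on the result is conditional. Following 7.2 on flutter, or the Appendix E header after a redo, can raise 12-month freedom or leave it unchanged; neither can lower it. Each patient reclassified moves the figure by 3.3 points. The total cannot be derived from the protocol. For the blanking restart, 0 to about 15 points is an illustration that rests on assumed recurrence (20–50%), redo share (25–50%) and same-interval share (30–60%, with 0 as the floor).

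This is a secondary endpoint in a single cohort. The primary endpoints, concordance of block and time to confirm it, are not affected, so it would be wrong to infer that the study's main conclusion is at risk.

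**What to change.** Use one definition in 3.2, 4.2, 7.2 and Appendix E: first documented AF, atrial flutter or AT of at least 30 seconds, after the 2-month blanking period counted from the index study procedure. In addition:

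- Add a CRF field for the date and type of any recurrence that prompted a redo, and count that recurrence even when the redo came before the visit at which the form is completed.
- Report rhythm after a redo separately, not as a fresh start of the 12-month curve.
- Remove 1 month from the freedom endpoint in 4.2, or label that result early recurrence.

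The cost is a few wording changes and a small CRF edit, best made before data are collected. Reported freedom may be slightly lower than under the literal wording.
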